Subjects may re-screen up to a maximum of two times, for a total of three Screening Visits. Each rescreen visit may only be initiated with the documented permission of the Medical Monitor in NESS. If a subject screen fails for knee radiography, rescreening is not recommended. For a full list of rescreening procedures and timelines, please see the protocol MOP.

F.1.5. Visit 1 – Baseline (Day 0)

For all visits, NEForm will be used to record the Patient Reported Outcome (PRO) scales. All other data will be directly entered into the study database or collected externally and entered into the EDC with source materials uploaded to Florence. Additional information and instructions on study activities can be found in the MOP.

- 1. Review NEForm collection procedures/compliance with subjects

Educate subjects to complete these forms. Subjects should try and complete at least 80% of remote procedures in NESS. If subjects fall below the 80% completion rate, retrain the subject at the next study visit.
- 2. Define index knee. Using the averaged screening period WOMAC-A scores by knee, the knee with the greater score at the end of screening is defined as the index knee going forward.
- 3. Review of inclusion and exclusion criteria to ensure that the patient meets the requirements for the study.
 - a) At the beginning of the visit, make sure subject did not take any prohibited medications or therapy prior to baseline.
 - b) At the end of the visit, confirm all criteria have been met prior to randomizing the subject.
- 4. Protocol Patient Measures – NEForm on Tablet
 - a) PROs

- WOMAC-A (Pain Scale)
- WOMAC-C (Functional Scale)

b) Staircase-Evoked Pain Assessment

5. NIH HEAL Initiative CDEs for chronic pain – NEForm

Optional: Participants and site staff may complete CDEs remotely to reduce time at the in-person clinic visit

- a) PEG Scale
- b) Pain Catastrophizing Scale – Short Form 6
- c) PROMIS Sleep Disturbance Scale – 6A
- d) Sleep Duration Question
- e) PROMIS Physical Functioning Short-Form 6b
- f) PHQ – Depression
- g) GAD-2
- h) TAPS-1
- i) OUQ

6. Lab Collection – enter data in EDC, upload reports for remote monitoring review

- a) Blood Draws:
 - i. Chemistry (See Schedule of Events footnotes for full list)
 - ii. Biomarkers – Cytokines & Chemokines (see section F.2.2)
- b) Urine Collection:
 - i. Full Urinalysis Panel
 - ii. Urine pregnancy test for WOCBP – EDC

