A patient who remains in the study for the first two treatment periods or for all four treatment periods will receive a balanced exposure to treatments randomized to receive. If patients discontinue treatment prior to completing the entire 24 weeks of study, all their data (including weekly assessments) from their time in the study will be used in the analyses. Because the main analysis is based on maximum likelihood estimation using a mixed-effects multi-period crossover model, the inferences will be unbiased under missing at random assumptions. No imputation of missing data is planned for this study, unless intensive investigations indicate that reliable and valid data imputation is possible, in which case multiple imputation will be performed and the analysis of the imputed data sets will serve as a sensitivity check of the results from the primary analysis based on the mixed-effects models (van Buuren et al, 2011).

All analyses will adjust for age, sex, K-L grade, and site.

All hypothesis tests will be two-sided using 5% significance level, and *p*-values unadjusted for multiple testing will be reported. The justification for this decision is that this is a Phase II investigation and all assessed outcomes are of specific and unique interest. Much more important than testing hypotheses is the efficient estimation of all quantities of interest, and this will be carried out throughout the analyses. Point estimates, 95% confidence intervals and standardized effect sizes (e.g., Cohen's *d*) will be reported for all estimated effects, regardless of whether the null hypotheses were rejected or not.

K.2. Hypothesis testing

Aim 1: Assess the safety of CNTX-6970 (300mg BID).

There will be no formal hypothesis testing under Primary Study Aim 1. All AEs and SAEs observed during different treatment periods will be summarized based on severity and relation to the active treatment (CNTX-6970 300mg BID). The reports will include tabulation of the AEs and SAEs by period, block, and treatment; point estimates and 95% CIs will be reported. Similarly, we will summarize relevant laboratory measures (see Section F.2.1) with appropriate estimates.

Aim 2: Assess the efficacy of CNTX-6970 (300mg BID) in comparison to placebo with respect to the primary outcome measure for pain due to osteoarthritis of the knee - WOMAC Part A.

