the relationship of the between-subject variability to the within-subject variability. In general, the between-subject variability is larger than the within-subject variability, but we investigated a range of Between/Within (B/W) variance ratios (5/1, 2/1). With a total sample size of $n=55$, there will be more than adequate power for the study using a two-sided Type I error rate of $\alpha=0.05$. A power analysis was conducted with $n=50$ and the power to detect an effect size (for an active treatment vs. placebo) of Cohen's $d=0.35$ is approximately 95% when the ratio B/W=2/1. Assuming a 15% early termination rate during each of the 4 periods will yield a sample size of $n=26$ with complete observations at all treatment periods for this simulation. If we conservatively assume that only subjects with complete data will be analyzed, the corresponding power with $n=26$ is approximately 81%. Because we will use all available data from all enrolled subjects in the analysis, the actual power in the case of 15% early termination rate per treatment period will be larger than 81%, and anywhere between 81% and 95%. If the ratio B/W is larger than 2, say B/W=3, 4 or 5, the power for detecting the treatment effects is much larger. For example, with only 26 patients, if B/W=5, the power to detect an effect of magnitude Cohen's $d=0.35$ is 0.96. Note that the reported test-retest reliability of the WOMAC-A measure is 0.86, which corresponds to a B/W=7.

[figure not shown]

Figure 2: Power versus Cohen's d effect size. B/W indicates the ratio of between-subject to within-subject variance of the WOMAC-A measure. Assuming that only data from completers will be used in the analysis gives a lower bound of the power that can be achieved for the given range of effect sizes.

■ PUBLICATION POLICY

See EPPIC-Net Publication Policy.

■ REFERENCES

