## 6 Sample Size

The sample size for this study was determined based on the primary efficacy aim to detect clinically meaningful and realistic effects of CNTX-6970 (300 mg BID) compared to placebo in the multi-period crossover

design model. Power was computed for effect sizes ranging from 0.25 to 0.50 using Monte Carlo simulation. Data were simulated from multi-period crossover models with block, period, and carryover effects, and varying within and between subject variability.

Although carryover effects can be efficiently isolated and estimated in the analysis stage by using the mixed-effects models proposed in Section 7, power for the primary hypothesis was computed using only WOMAC-A assessed during the last 2 of 6 weeks per treatment period to minimize carryover effects. The power of the test depends on the relationship of the between-subject variability to the within-subject variability. In general, the between-subject variability is larger than the within-subject variability, but a range of Between/Within (B/W) variance ratios (5/1, 2/1) were investigated. With a sample size of  $n = 55$  per arm, using a two-sided Type I error rate of  $\alpha = 0.05$ , the power to detect an effect size (for the active treatment vs. placebo) of Cohen's  $d = 0.35$  exceeds 95% when the ratio  $B/W = 2/1$ .

Assuming a 15% early termination (e.g., dropout) rate during each of the 4 periods will yield a sample size of approximately  $n = 29$  with complete observations at all treatment periods. If we conservatively assume that only subjects with complete data will be analyzed, the corresponding power with  $n = 29$  exceeds 80% when the ratio  $B/W = 2/1$  with an effect size as low as 0.30. Figure 2 shows the results of a simulation study to evaluate the power of this design. Because we will use all available data from all enrolled subjects in the analysis, the actual power in the case of 15% early termination per treatment period will be larger than what Figure 2 shows. If the ratio B/W is larger than 2, say B/W=3, 4 or 5, the power for detecting the treatment effects is much larger. For example, with only 29 participants, if B/W=5, the power to detect an effect of magnitude Cohen's  $d = 0.35$  exceeds 0.95. Note that the reported test-retest reliability of the WOMAC-A measure is 0.86, which corresponds to a  $B/W = 7$ .

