### 9.1 Primary Efficacy Analysis

For the efficacy Aim 2, data from the WOMAC Part A (WOMAC-A) assessed only in the last two weeks of each 6-weeks treatment period will be used for this primary analysis in order to avoid any carryover effects, which are expected to vanish after 4 weeks. Hypothesis 1 in Section 4 will be tested using the following random-effects multi-period crossover model that employs block and period effects to compare the active treatment to placebo (Zucker *et al.*, 1997; Chen and Chen, 2014). Specifically, the model is:

$$y_{i(s)jkm} = \beta_0 + \gamma_j + \delta_k + \beta_1 X_{i(s)jk} + \beta_2' \mathbf{w}_{i(s)} + b_s + b_{i(s)} + \epsilon_{i(s)m}, \quad (1)$$

where  $i(s)$  is the index for patient  $i$  at site  $s$ ;  $\beta_0$  is the intercept;  $j$  is the index for block,  $j = 1, 2$  and  $\gamma_j$  is the block effect;  $k$  is the index for period,  $k = 1, 2$ , and  $\delta_k$  is the period effect;  $m$  is the measurement time;  $y_{i(s)jkm}$  is the primary outcome for subject  $i(s)$ , block  $j$ , period  $k$ , time  $m$ ;  $\beta_1$  represents the treatment effect, and  $X_{i(s)jk}$  is an indicator for active treatment ( $X_{i(s)jk} = 1$ ) or placebo ( $X_{i(s)jk} = 0$ ) for patient  $i(s)$ , in block  $j$ , during period  $k$ ;  $\mathbf{w}_{i(s)}$  is a vector of baseline characteristics (e.g., age, sex, K-L grade indicator) for patient  $i(s)$  and  $\beta_2$  is a vector of coefficients for those baseline characteristics;  $b_s \sim N(0, \sigma_{site}^2)$  is a random site effect and  $b_{i(s)} \sim N(0, \sigma_b^2)$  is a subject-level random effect (nested within site);  $\epsilon_{i(s),m}$  is a random error with an  $AR(1)$  structure:  $\epsilon_{i(s),m} = \phi \epsilon_{i(s),m-1} + u_{i(s)m}$ , with  $u_{i(s)m} \sim N(0, \sigma_u^2)$ . The subject-level random effects will model the repeated measures within subjects. The block and period effect terms will accommodate changes in mean pain scores across blocks and periods of the design.

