For PGIC, this instrument asks if the overall pain since the start of the study is “Very much improved” (score 0), “Much improved” (score 1), “Minimally improved” (score 2), “No Change” (score 3), “Minimally worse” (score 4), “Much worse” (score 5), “Very much worse” (score 6). The analysis for outcome (c) PGIC will use a proportional odds regression with outcome PGIC at week 24 (V9), controlling for treatment, age, sex and baseline WOMAC-A; this model will not control for week 3 PGIC since the instrument is asking about the change in pain. Note also that the treatment in the last period is the same treatment as in the first period, so a comparison of the active to the placebo in terms of change in pain can be done using week 24 PGIC outcomes for the two different treatment sequences used in this trial. The analysis plan for outcome (e) will follow the same approach as in aim 4 below.

**Aim 4.** Outcomes (a)-(f) are assessed at baseline and week 24. Testing hypotheses for these outcomes will not benefit from the multi-period crossover design because they are assessed only at baseline and week 24. Instead, we will test the hypotheses by comparing subjects taking active drug versus placebo at the last treatment period ending on week 24. Regressions will be used to model the outcome at week 24 as a function of treatment, the baseline level of the outcome, age, sex and K-L Grade. A standard linear regression will be used for continuous outcomes; a proportional odds model will be used for the non-binary ordinal outcomes defined by discrete categories (e.g., PHQ-2, GAD) and logistic regression models will be used for binary outcomes (e.g., OUQ).

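### The primary model does not name baseline WOMAC-A as a covariate; adding it costs nothing and takes about 1–2% off the standard error

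*SAP*

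**What the plan says.** Model (1) in SAP 9.1 has block, period and treatment effects, a random site effect, a random patient intercept and a covariate vector w. The SAP describes w as "a vector of baseline characteristics (e.g., age, sex, K-L grade indicator", so the list is open. SAP 7.3 and protocol K.1 name K-L grade, age, sex and site for all analyses. Neither names baseline WOMAC-A.

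The scores exist. Protocol E.4.1 (criterion 10) requires at least four WOMAC-A assessments during screening. Protocol F.1.5 picks the index knee "Using the averaged screening period WOMAC-A scores by knee", and the Schedule of Events has a further WOMAC-A at Visit 1.

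Elsewhere the SAP does use baseline values. The PGIC model in SAP 9.2 is fitted "controlling for treatment, age, sex and baseline WOMAC-A". SAP 7 adjusts outcomes recorded only at baseline and week 24 for their own baseline.

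On loss to follow-up, SAP 6 states: "Assuming a 15% early termination (e.g., dropout) rate during each of the 4 periods will yield a sample size of approximately" 29 patients with complete data. SAP 7.4 relies on maximum likelihood under missing at random, with imputation only as a contingent sensitivity check.

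**The concern.** In a crossover model with a patient intercept, a patient's own pain level cancels out of the treatment comparison when that patient gives balanced data on both treatments. It does not cancel for a patient who gives one period only. That patient's score informs the treatment effect only by comparison with other patients, so between-patient variance enters in full. A pre-treatment measure of the same scale is the obvious way to remove part of it.

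There is also a missing-data side. If withdrawal depends on baseline pain, the analysis is safer when it conditions on baseline pain. Leaving it out means relying on a somewhat stronger missing-at-random assumption than the collected data require.

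At stake are a little precision in the primary test and a little robustness to dropout.

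**Working it through.** **Inputs.**
- Total n = 55 (protocol K.4: "With a total sample size of $n=55$, there will be more than adequate power"). SAP 6 speaks of 55 per arm; the protocol total is used here.
- Sequences DPPD and PDDP, 1:1 (SAP 5.3).
- Loss of 15% in each of four periods, and B/W of 2 and 5, with 7 quoted from reliability (SAP 6).
- Two-sided 5% test (protocol K.1).
- Assumed, not in the documents: d is scaled to the total SD; one value per period; a patient lost in a period gives no week 5–6 score in it; B/W also sets the correlation between baseline and outcome.

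**1. The plan's completer count.** 55 × 0.85⁴ = 28.7, which reproduces the SAP's 29.

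**2. The plan's completer power.** With four balanced periods, SE² = σ_w²/n. With total variance 1 and B/W = 2, σ_b² = 2/3 and σ_w² = 1/3. For n = 29, SE = √(0.3333/29) = 0.1072. Power at d = 0.30 is Φ(0.30/0.1072 − 1.96) = 79.9%; the SAP says above 80%, "with an effect size as low as 0.30". For n = 29, B/W = 5 and d = 0.35 it is 99.6% (SAP: above 0.95).

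The protocol's n = 50 figure, "Cohen's $d=0.35$ is approximately 95% when the ratio B/W=2/1", is not matched: this method gives 99.0%. No single variant tried matched all three of the protocol's power figures. The absolute powers below therefore depend on the scaling of d. The percentage change in SE does not.

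**3. Dropout patterns.**

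| Periods contributed | Share | Of 55 |
|---|---|---|
| 0 | 15.0% | 8.3 |
| 1 | 0.85 × 0.15 = 12.8% | 7.0 |
| 2 | 0.85² × 0.15 = 10.8% | 6.0 |
| 3 | 0.85³ × 0.15 = 9.2% | 5.1 |
| 4 | 0.85⁴ = 52.2% | 28.7 |

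**4. SE with and without baseline.** SE² is the treatment element of [Σ n_p X_p′V_p⁻¹X_p]⁻¹, summed over sequences and dropout patterns, with V = σ_b²J + σ_w²I and additive block and period effects. Adjusting for the mean of K baseline scores replaces σ_b² by σ_b²(1 − ρ), where ρ = σ_b²/(σ_b² + σ_w²/K). At B/W = 2, ρ = 0.667 for K = 1 and 0.909 for K = 5. The variance of a lone score then falls from 1.000 to 0.556 or 0.394.

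| B/W | SE, no baseline | SE, one score | SE, mean of five |
|---|---|---|---|
| 2 | 0.0966 | 0.0959 (−0.8%) | 0.0951 (−1.5%) |
| 5 | 0.0686 | 0.0679 (−1.1%) | 0.0673 (−1.9%) |
| 7 | 0.0595 | 0.0588 (−1.1%) | 0.0583 (−2.1%) |

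At B/W = 2 and d = 0.30, power goes from 87.4% to 87.9% (one score) or 88.4% (five). A perfect baseline would give 88.7%. The variance reductions at B/W = 2 are 1.5% and 3.0%, worth 0.015 × 55 = 0.8 and 0.030 × 55 = 1.7 patients. At B/W = 5 or 7, power already exceeds 99%.

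With two values per period and AR(1) correlation of 0 or 0.5, the one-score variance reduction stays within 1.3–2.3% and the upper bound (perfect baseline) is 5.5%.

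**5. Where the gain comes from.** Dropping the one-period patients from the calculation leaves an SE gain of 0.11–0.14% with one score and 0.30–0.35% with five. With only two- and four-period patients the gain is zero.

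**6. Missing at random.** This was simulated with 3,000 trials per scenario; the Monte Carlo error of the bias is about 0.002 SD.

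| Dropout depends on | Bias, no baseline (SD) | Bias, with baseline (SD) |
|---|---|---|
| nothing | −0.0008 | −0.0008 |
| baseline pain | 0.0012 | 0.0011 |
| previous score | 0.0026 | 0.0024 |
| baseline pain, placebo periods only | 0.0144 | 0.0015 |

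The last scenario is assumed, not taken from the documents. Its bias without adjustment is 0.0144/0.30 = 5% of an effect of 0.30.

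**The case against.** The strongest reply is that model (1) already handles a patient's pain level through the random intercept, and that the mixed model conditions on earlier WOMAC-A scores, so a baseline covariate is a matter of taste worth about half a power point. Most of this stands. The gain is nil for balanced patients, it is small overall, and bias differs only in the one assumed scenario where dropout depends jointly on baseline pain and treatment. The entry rule in SAP 5.2 (screening mean 20–45 in at least one knee) probably weakens the baseline-to-outcome correlation, so the gains above are likely upper values. Protocol F.3.2 also keeps some patients under assessment after they stop drug, which could change the dropout mix. None of this argues against a covariate that needs no new data.

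Three stronger readings are tempting and are not supported:

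- **That about half of patients benefit, because 47.8% are incomplete.** That share includes 15% with no primary score and 10.8% with two balanced periods, neither of whom gain. The benefit comes mainly from the 12.8% with one period.
- **That the SAP contradicts itself by adjusting PGIC for baseline WOMAC-A.** PGIC is a single week-24 comparison between sequences and has no baseline of its own. SAP 7 ties baseline adjustment to outcomes recorded only at baseline and week 24. Treating a within-patient analysis differently is a defensible rule.
- **That the SAP excludes baseline WOMAC-A.** The list for w is given by example, so the covariate is unnamed, not ruled out.

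**Conclusion.** The point holds as a free improvement to the primary model. Baseline WOMAC-A is available in every randomised patient and is not named in model (1), SAP 7.3 or protocol K.1. Under the planned dropout, naming it would reduce the SE by about 0.8–1.1% with one score or 1.5–2.1% with the mean of five, roughly 0.5–1 power point at d = 0.30 and B/W = 2.

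These sizes rest on 15% loss per period, one value per period, and B/W also governing how well baseline predicts later scores. A reader might infer that the primary analysis is biased or underpowered without baseline. The documents do not support that: under these assumptions the power is 87.4% without it, and bias is negligible unless dropout depends on both baseline pain and treatment.

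**What to change.** Before unblinding:

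1. In SAP 9.1, replace the open example list for w with a closed list, and add index-knee baseline WOMAC-A to it for model (1). Define it as the mean of the pre-randomisation screening scores and the Visit 1 score; in the calculation, a mean of five gives about twice the gain of a single score.
2. Add the same covariate to model (3) once the role of the Day 0 score is settled. That model takes week 6 of the preceding period as the next period's baseline, and the corresponding value for period 1 needs stating first.
3. For the other outcomes fitted with model (2), use each outcome's own pre-treatment value where one is collected, not WOMAC-A.
4. Align SAP 7.3 and protocol K.1 with the final list.

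The cost is one coefficient in the primary model and a few lines of text. No new data are needed.

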## 5.3 Randomization and Blinding

For entry into the study and randomization, all eligibility criteria MUST be met (i.e., all inclusion criteria and no exclusion criteria specified in the protocol). Patients who meet inclusion/exclusion criteria at the Baseline Visit (day 0) will be randomized. After documentation of written informed consent and the screening period, clinical sites will confirm eligibility and complete randomization by accessing the Almac's centralized web-based system for randomization and drug management - the Interactive Web Response System (IXRS). Subjects will be randomized equally between treatment sequences shown in Figure 1: Drug:Placebo:Placebo:Drug or Placebo:Drug:Drug:Placebo. A standard block randomization will be used, stratifying by K-L grade (stratum 1 K-L grade 1 or 2, and stratum 2 K-L grade 3 or 4) to achieve balance on randomization sequences. The randomization will be implemented by the IXRS vendor in consultation with the study statisticians. After Randomization, drug will be dispensed.

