The primary hypothesis of interest for this model is  $H_0 : \beta_1 = 0$  versus  $H_a : \beta_1 \neq 0$ . Maximum likelihood estimation will be used to estimate the model parameters using the statistical software R and likelihood ratio tests will be performed to test and obtain  $p$ -values for the hypotheses of treatment effects (active versus placebo) for the active treatment. Under the null hypothesis, the likelihood ratio test will have an approximate chi-square distribution with 1 degree of freedom. The hypothesis testing proposed here is based on the WOMAC-A assessed only in the last 2 weeks of each 6-week treatment period. This provides a more than adequate 4-week washout interval for CNTX-6970. The adequacy of this 4-week period is based on extensive pharmacokinetics (PK) and pharmacodynamics (PD) of the study agent CNTX-6970 provided in the Centrexion dossier.

Additionally, for the analysis under Aim 3 described below, we explicitly model the potential carryover effects using model (2),

The proposed model (2) utilizes a standard approach to adjust for carryover effects in a multi-period crossover design when estimating the treatment effect, and allows for testing for the existence of carryover effect (Chen and Chen, 2014).

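### Model (1)'s additive block and period terms omit the one time contrast that matches the treatment pattern, so a curved trend can shift the drug estimate slightly if the sequences become unbalanced

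*SAP*

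**What the plan says.** Section 9.1 of the SAP tests the drug effect, beta1, with a "random-effects multi-period crossover model that employs block and period effects to compare the active treatment to placebo". Block has two levels (gamma_j) and period within block has two levels (delta_k). They enter as main effects, with no block-by-period term. The SAP's account of these terms is that "The block and period effect terms will accommodate changes in mean pain scores across blocks and periods of the design". The data are WOMAC-A scores "assessed only in the last two weeks of each 6-weeks treatment period", and for the test of beta1 "the likelihood ratio test will have an approximate chi-square distribution with 1 degree of freedom".

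Section 5.3 names two sequences, "Drug:Placebo:Placebo:Drug or Placebo:Drug:Drug:Placebo" (DPPD and PDDP below). It adds that "Subjects will be randomized equally between treatment sequences shown in Figure 1" and that "A standard block randomization will be used, stratifying by K-L grade"; the size of the randomization blocks is not stated. Section 9.2 confirms that "the treatment in the last period is the same treatment as in the first period".

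Section 6 assumes 15% early termination in each of the four periods. Section 7.4 keeps a patient's data up to discontinuation. Models (2) and (3), in sections 9.2 and 9.3, reuse the same additive terms.

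**The concern.** Four period means carry three degrees of freedom for time, and two additive two-level factors use two of them. What is left out is the contrast between the outer periods (1 and 4) and the inner periods (2 and 3). In DPPD the drug is given in the outer periods, and in PDDP in the inner ones, so the omitted time contrast has exactly the shape of the treatment indicator.

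The two sequences carry it with opposite signs, and it cancels if they contribute equally. If they do not, part of a time effect is read as a drug effect, because nothing else in the model can take it up. Balance at randomization is well protected. Balance in the analysed data is less so: with 15% loss per period, only about half of those randomized are expected to complete all four periods, and partial sequences stay in the likelihood. Neither document plans a check for this.

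**Working it through.** **Inputs from the documents.** Sequences DPPD and PDDP, allocated equally (SAP 5.3); additive block and period terms (SAP 9.1); total n = 55, d = 0.35, between/within variance ratio B/W = 2 and 15% loss per period (SAP 6; Protocol K.4 also gives 55 as the total).

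**Assumptions, not in the documents.** Total SD = 1, so the within-subject variance is 1/(1+2) = 1/3; two weekly scores per period; AR(1) correlation 0.5 between weekly errors unless stated; the period means.

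**The plan's own figures.** Completers: 55 × 0.85^4 = 28.7 (29 stated). Power at d = 0.35 with one score per period: SE = sqrt((1/3)/55) = 0.078, and Phi(0.35/0.078 - 1.96) = 0.994. With two independent scores the SE is 0.055 and power is above 0.999. The stated figure of more than 95% is reproduced.

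**Aliasing.** Let c = (+1,-1,-1,+1), the contrast orthogonal to the intercept, block and period. Then X = 0.5 + 0.5c in DPPD and X = 0.5 - 0.5c in PDDP. A straight-line trend has no component along c.

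**Size of the shift.** Let mu1 to mu4 be the period means without drug, and Delta = [(mu1+mu4) - (mu2+mu3)]/2. A complete DPPD patient's drug-minus-placebo difference has expectation beta1 + Delta; a PDDP patient's has beta1 - Delta. The additive model pools patients with equal weight:

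expected estimate = beta1 + Delta × (nA - nB)/(nA + nB), with nA on DPPD and nB on PDDP.

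A four-level period factor instead averages the two sequences equally, so Delta cancels. With r = (nA - nB)/(nA + nB), its SE is larger by the factor 1/sqrt(1 - r^2).

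**Illustrative Delta.** Means (0, -0.3, -0.4, -0.4) SD give Delta = (-0.4 + 0.7)/2 = 0.15. Means (0, -0.4, -0.4, -0.4) SD give (-0.4 + 0.8)/2 = 0.20.

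| Complete sequences | r | Shift, Delta 0.15 to 0.20 | Share of d = 0.35 | SE increase with the fix |
|---|---|---|---|---|
| 27.5:27.5 (exact balance) | 0 | 0 | 0 | 0 |
| 28:27 (equal allocation of 55) | 0.018 | 0.003 to 0.004 SD | about 1% | under 0.1% |
| 30:25 (assumed split) | 0.091 | 0.014 to 0.018 SD | 4 to 5% | 0.4% |
| 16:13 completers (assumed) | 0.103 | 0.016 to 0.021 SD | 4 to 6% | 0.5% |
| 17:12 completers (assumed) | 0.172 | 0.026 to 0.034 SD | 7 to 10% | 1.5% |

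Generalised least squares for model (1) reproduces every shift in the table. It gives zero for a linear trend in every case tried, and zero for any trend once the four-level factor is used.

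**Planned dropout.** Starting from 28:27, with random 15% loss per period and all data kept, the shift has root mean square about 0.013 to 0.019 SD and mean about 0.003 SD. The model SE is about 0.084 (0.0836 additive, 0.0840 with the four-level factor). With independent weekly errors, the average type I error under the additive model is 5.2% at Delta = 0.1 and 5.8% at Delta = 0.2.

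**Dropout that depends on treatment or sequence** (independent weekly errors). At 20% per period on drug and 10% on placebo the shift is 0.007 × Delta, about 0.001 SD, because each sequence has two periods of each treatment. At 20% per period in one sequence and 10% in the other it is 0.158 × Delta, or 0.024 to 0.032 SD.

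**The case against.** The strongest reply is that the additive model is pre-specified, the allocation is equal and blocked within two K-L strata, and the effect is small. Most of this stands. At 28:27 the shift is about 1% of the design effect. Dropout that depends on treatment nearly cancels. Chance imbalance has no fixed direction, so it behaves as extra noise, and the fix lowers total root-mean-square error by only about 1 to 2%. The 30:25 split is an assumption: randomization blocks of four in two strata could not produce it, though the block size is not stated.

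A reader might infer that time trends in general leak into the drug effect. They do not: linear drift and any sum of a block shift and a period shift are fully absorbed. A reader might also call the SAP sentence untrue. It describes the two main effects correctly and does not claim to fit all four period means; it is incomplete. Nor is there much in the thought that the omitted contrast widens the interval even when balanced: at Delta = 0.2 (an amplitude of 0.1 SD along c) it adds 0.01/(1/3) = 3% to the residual variance, about 1.5% to the SE at most.

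One dependency remains. Protocol section D.1 describes randomizing the two treatments to the periods within each block, which could allow four sequences. The aliasing would then be only partial. The SAP is explicit that there are two, but the texts should be reconciled.

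**Conclusion.** The point holds at low severity. The aliasing is exact for the two SAP sequences, and the formula for the shift is exact for complete sequences. Its size rests on an assumed Delta, because neither document gives period means, and on the imbalance that dropout happens to produce. For Delta of 0.15 to 0.20 SD the shift runs from nothing under balance to about 0.034 SD at 17:12 completers. Under the planned dropout it is mainly chance error, small beside the standard error.

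The documents do not support the stronger reading that the primary estimate is systematically biased. A shift of consistent direction needs dropout that differs by sequence, and neither document gives a reason to expect that. Power and the main conclusion are not threatened. The case for acting is that the safeguard costs almost nothing and makes the SAP's description of the model complete.

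**What to change.** In model (1), replace gamma_j + delta_k with a four-level period factor or, equivalently, add the block-by-period term. Carry the change into models (2) and (3) so that the mean structure is the same throughout. Amend the sentence in SAP 9.1 to say that all four period means are fitted.

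The cost is one degree of freedom and one line of the SAP. For model (1) the SE is unchanged under exact balance, about 0.4% higher under the expected dropout and about 1.5% higher at 17:12. Power at d = 0.35 is 0.9988 rather than 0.9989 (independent weekly errors, 15% dropout per period). The change should be made before unblinding, so that no choice between the two models is left until after the data are seen.

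Separately, reconcile Protocol D.1 with SAP 5.3 on whether two or four sequences are used.
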